12.0 ADVERSE EVENTS

All patients who receive at least one study injection or another study-related procedure will be considered evaluable for safety parameters. This includes any untoward signs (including abnormal laboratory findings) or symptoms experienced by the patient from the time of enrollment until the EOS / Post Vaccination Safety Visit (i.e., last study visit before long-term follow-up). For patients enrolled on the pembrolizumab arm, all AEs experienced from the time of enrollment through 30 days following cessation of treatment will be reported by the investigator. Safety will be evaluated for all treated patients using the *NCI CTCAE v.4.03* or newer. Safety assessments will be based on medical review of both solicited and spontaneously reported AEs, including symptoms, physical examination findings, vital signs, laboratory findings, ECGs, and discontinuations for AEs. The nature, severity, and frequency of AEs will be monitored on an ongoing basis for risk assessment and to determine if risk management interventions are warranted (i.e., expedited notification of safety findings to investigators, IRBs or regulators; update of IB and ICF risks and re-consenting study patients; revision of safety monitoring procedures; revision of eligibility criteria or other study procedures; etc.).

Progression of the cancer under study is not considered an AE unless it is considered to be drug-related by the investigator.

All SAEs that are unexpected and considered possibly, probably or definitely related to study regimen will be reported to the FDA and IRB in accordance with the requirements in 21 code of federal regulations (CFR) §312.32.

12.1 Definitions

Adverse Event (AE) - Any untoward medical occurrence in a patient or clinical investigation patient administered a pharmaceutical product, medical treatment or procedure and which does not necessarily have to have a causal relationship with this regimen. An AE can therefore be any unfavorable and unintended sign (including an abnormal laboratory finding, for example), symptom, or disease temporally associated with the use of a medicinal product, medical treatment or procedure whether or not considered possibly, probably or definitely related to the medicinal product.

Unexpected Adverse Event – An AE is “unexpected” when its nature (specificity), severity, or frequency are not consistent with the known or foreseeable risk of AE associated with the research procedures described in the protocol, informed consent form, or the investigator brochure.

Serious Adverse Event (SAE) – Any AE occurring that results in any of the following outcomes:

- 1) Death.
- 2) A life-threatening AE.
- 3) Inpatient hospitalization or prolongation of existing hospitalization.
Note: Hospitalizations not to be reported as SAEs include admissions for planned medical/surgical procedure (such as scheduled tumor excision or debulking surgery) or routine health assessment requiring admission for baseline/trending of health status documentation (e.g., routine colonoscopy) or admission for social purposes such as lack of housing, economic inadequacy, care-giver respite, or family circumstances.
- 4) A persistent or significant disability/incapacity.
- 5) Results in a congenital anomaly/birth defect.
- 6) Is a medically important condition which is judged by a health care professional as serious.

The term “life-threatening” refers to an event in which the subject was at risk of death at the time of the event, and it does not refer to an event that hypothetically might have caused death if it were more severe.

Disability refers to a substantial disruption of a person’s ability to conduct normal life function.

Medical and scientific judgment will be exercised in deciding whether expedited reporting is appropriate in other situations, such as important medical events that may not be immediately

life-threatening or result in death or hospitalization but may jeopardize the subject or may require intervention to prevent one of the outcomes listed in the definition above. These may also be considered serious. Examples of such events are intensive treatment in an emergency room or at home for allergic bronchospasm; or blood dyscrasias or convulsions that do not result in hospitalization.

When there is doubt regarding an AE meeting the criteria for an SAE, the investigator should default to reporting the AE as an SAE.

There are special circumstances in which an SAE reporting form is used to communicate important clinical trial safety observations that may not constitute an SAE.

- 1) Pregnancy: Although pregnancy is not considered an SAE and is instead a normal human experience, all pregnancies reported in the month before or month after last G100 investigational injection must be reported to Sponsor. If enrolled onto the pembrolizumab arm, pregnancies and lactations that occur through 120 days following cessation of pembrolizumab or 30 days if the subject initiates new anticancer therapy, whichever is earlier, must be reported by the investigator. (See [Section 12.7](#))
- 2) Overdose: As defined for this study, an overdose is defined as the accidental or intentional administration of any dose of the G100 product that is considered both excessive and medically important. For reporting purposes, an overdose will be considered, regardless of adverse outcome, as an important medical event. All cases of overdose must be reported immediately to the Sponsor.
- 3) Definition of an Overdose for This Protocol and Reporting of Overdose to the Sponsor for Pembrolizumab. For this trial, an overdose will be defined as ≥ 1000 mg (5 times the dose) of pembrolizumab. No specific information is available on the treatment of overdose of pembrolizumab. In the event of overdose, the subject should be observed closely for signs of toxicity. Appropriate supportive treatment should be provided if clinically indicated.

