7.1 Inclusion Criteria

In order to be enrolled in the study, patients must meet **all** of the following inclusion criteria:

- 1) Follicular low-grade NHL (grades 1, 2, 3A): either treatment naïve or relapsed or refractory following at least one prior treatment. For France, patients with either relapsed or refractory only. In Part 1 Dose Escalation only, in addition to follicular NHL, marginal zone B cell lymphomas: either treatment naïve or relapsed or refractory following at least one prior treatment.
 - In Part 4, enrollment is limited to relapsed or refractory follicular NHL patients who have received at least 3 prior systemic treatments, one of which was or included an anti-CD20 antibody.
 - In Part 5, enrollment will include relapsed or refractory CD20+ follicular NHL following at least one but not more than 2 prior treatments.
- 2) Tumor mass(es) accessible for intratumoral injection and are being considered for local radiation therapy and at least one additional site of disease outside the radiation field for assessment of distal (abscopal) response. (Imaging assisted injections are allowed following approval by Medical Monitor)
 - For Parts 4 and 5, radiation therapy is omitted. Measurable tumor mass(es) accessible for intratumoral injection must be present for treatment and assessment of response.
- 3) ≥ 18 years of age
- 4) Life expectancy of ≥ 6 months per the investigator
- 5) Eastern Cooperative Oncology Group (ECOG) performance status of 0 or 1
- 6) ECG without evidence of clinically significant arrhythmia or ischemia
- 7) If female of childbearing potential (FCBP), willing to undergo pregnancy testing and agrees to use two methods of birth control or is considered highly unlikely to conceive during the dosing period and for three months after last study treatment, or if receiving pembrolizumab, four months after last treatment (See [Section 8.1.9](#) and [Appendix F: References for details](#))
- 8) If male and sexually active with a FCBP, must agree to use effective contraception such as latex condom or is sterile (e.g., following a surgical procedure) during the dosing period and for three months after last study treatment, or if receiving pembrolizumab, four months after last treatment (See [Section 8.1.9](#) and [Appendix F: References for details](#))

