8.1.9 Contraception

G100, rituximab and/or pembrolizumab may have adverse effects on a fetus in utero.

Furthermore, it is not known if G100 and/or pembrolizumab have transient adverse effects on the composition of sperm.

Subjects should be informed that taking the study medication may involve unknown risks to the fetus (unborn baby) if pregnancy were to occur during the study. Therefore, non-pregnant, non-breast-feeding FCBP may only be enrolled if they are willing to use 2 methods of birth control or are considered highly unlikely to conceive. Highly unlikely to conceive is defined as 1) surgically sterilized, or 2) postmenopausal (a woman who is ≥ 45 years of age and has not had menses for greater than 1 year will be considered postmenopausal), or 3) not heterosexually active for the duration of the study. Abstinence is only acceptable as “true abstinence” when it is in line with the preferred and usual lifestyle of the patient and not a periodic occurrence (see [Appendix F](#)). The two birth control methods can be either two barrier methods or a barrier method plus a hormonal method to prevent pregnancy. Subjects should start using birth control from study Visit 1 throughout the study period up to 120 days after the last dose of study therapy if receiving pembrolizumab or at least 90 days if only receiving G100.

The following are considered adequate barrier methods of contraception: diaphragm, condom (by the partner), copper intrauterine device, sponge, or spermicide as per local regulations or guidelines. Appropriate hormonal contraceptives will include any registered and marketed contraceptive agent that contains an estrogen and/or a progestational agent (including oral, SC,

intrauterine, or IM agents). See [Appendix F](#) for additional details and definitions of highly effective agents.

For male patients, acceptable contraception includes documented sterility such as what is achieved following surgical sterilization (vasectomy or orchiectomy) or use of male condom. If the partner is a woman of childbearing potential, supplemental contraception with hormonal or barrier methods should be considered.

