8.1.10 Use in Pregnancy

If a subject inadvertently becomes pregnant while on treatment with G100, rituximab and/or pembrolizumab, the subject will immediately be removed from the study. The site will contact the subject at least monthly and document the subject's status until the pregnancy has been completed or terminated. The outcome of the pregnancy will be reported to the Sponsor without delay and within 24 hours if the outcome is a serious adverse experience (e.g., death, abortion, congenital anomaly, or other disabling or life-threatening complication to the mother or newborn). The study investigator will make every effort to obtain permission to follow the outcome of the pregnancy and report the condition of the fetus or newborn to the Sponsor. If a male subject impregnates his female partner the study personnel at the site must be informed immediately and the pregnancy reported to the Sponsor and followed as described above and in [Section 12.7](#).

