## **5 Statistical Analysis**

### **5.1 Data Summaries and Conventions**

All data collected on case report forms will be provided in listings, except data collected only for confirmation of study entry criteria and for study administrative purposes. If any enrolled patient is found to not have valid documented informed consent, that patient's data will be excluded from the report, except as necessary to document the error.

Except where specified all continuous variables will be summarized with descriptive statistics (the number of non-missing values, mean, standard deviation, median, minimum and maximum) and all categorical variables will be summarized with frequency counts and percentages, by part, treatment, and overall.

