### **5.7.8 Pregnancy Test**

Pregnancy test results will be presented in a listing.

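### For women not on pembrolizumab, the dated duty to report a pregnancy to the Sponsor ends about one month after the last G100 injection, while contraception is required for three months

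*Protocol*

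**What the plan says.** **Reporting window.** For patients not on pembrolizumab, Protocol 12.1 states that "all pregnancies reported in the month before or month after last G100 investigational injection must be reported to Sponsor". The same item gives the pembrolizumab arm 120 days, cut to 30 if new anticancer therapy starts. Section 12.4 repeats the 120 days under a pembrolizumab heading and has no matching line for other patients.

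**Contraception period.** Inclusion criteria 7 and 8 in 7.1 require contraception "during the dosing period and for three months after last study treatment", extended to four months with pembrolizumab. Section 8.1.9 sets 120 days with pembrolizumab "or at least 90 days if only receiving G100"; it does not name G100 plus rituximab. It also refers to a follow-up period defined in 12.7, but 12.7 defines none for patients not on pembrolizumab.

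**Pregnancy on treatment, and partners.** Section 8.1.10 deals with a subject who "becomes pregnant while on treatment with G100" (or rituximab or pembrolizumab), and says "The outcome of the pregnancy will be reported to the Sponsor without delay". If a male subject's partner conceives, site personnel "must be informed immediately and the pregnancy reported to the Sponsor and followed"; this has no time limit.

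**Section 12.7.** A one-month sentence, incomplete as written, calls for discontinuation and investigator follow-up and does not mention the Sponsor. Later sentences on follow-up and 24-hour outcome reporting refer to all subjects, but sit in a paragraph that opens with patients receiving pembrolizumab.

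**Test results.** SAP 5.7.8 says "Pregnancy test results will be presented in a listing", and SAP 5.1 says "All data collected on case report forms will be provided in listings", apart from entry-criteria and administrative data.

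**The concern.** Section 8.1.9 says that G100 and rituximab may harm a fetus, and the protocol accordingly asks women to avoid pregnancy for three months. A reporting window that covers only the first month leaves about two thirds of that period without a clear instruction to tell the Sponsor. Long-term follow-up for these patients collects possibly related SAEs, and 12.1 says that pregnancy itself is not an SAE. The follow-up visit lists (10.3.10.1, 10.3.28, 10.3.29.1) contain no pregnancy test.

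At stake are early data on fetal exposure to a new agent and a new combination, which could arrive late or incomplete. These are conceptions after dosing ends, so exposure is lower than for conceptions on treatment.

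**Working it through.** The documents give no figure to reproduce; this is a day count. One month is taken as 30 days.

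**Inputs.** Reporting window: 30 days after last G100 (12.1). Contraception: 90 days after last treatment (7.1, 8.1.9). Dose days and tests: Schedules of Events 3.2, 3.4 and 3.6. Last scheduled first-course test: Day 77 in Parts 1 to 3. In Part 5 it is Day 56 (3.6, 10.3.27), although 10.3.26 mentions Day 77. Windows (10.1): doses ±2 days, follow-up visits ±7 days.

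**Step 1: the gap.** 90 − 30 = 60 days (days 31 to 90), or 60/90 = two thirds. For pembrolizumab, 120 − 120 = 0, unless new anticancer therapy starts. Whether 12.1 refers to the date of report or the date of pregnancy, a conception on days 31 to 90 falls outside.

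**Step 2: days left once both the reporting window and the last scheduled test have passed.** Days left = (last G100 day + 90) − the later of (last G100 day + 30) and the test day.

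| Part | G100 doses | Last G100 | Window closes | Test | Contraception ends | Days left |
|---|---|---|---|---|---|---|
| 1–3 | 6 | Day 35 | Day 65 | Day 77 | Day 125 | 48 |
| 1–3 | 7 | Day 42 | Day 72 | Day 77 | Day 132 | 55 |
| 1–3 | 8 | Day 49 | Day 79 | Day 77 | Day 139 | 60 |
| 1–3 | 9 | Day 56 | Day 86 | Day 77 | Day 146 | 60 |
| 5 | 4 | Day 21 | Day 51 | Day 56 | Day 111 | 55 |
| 5 | 5 | Day 28 | Day 58 | Day 56 | Day 118 | 60 |
| 5 | 6 | Day 35 | Day 65 | Day 56 | Day 125 | 60 |

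If the Part 5 test in 10.3.26 is done on Day 77, the last three rows become 111 − 77 = 34, 118 − 77 = 41 and 125 − 77 = 48. The Part 5 schedule has no Day 77 visit, so the text does not settle which applies. The 60 days in Step 1 do not depend on it.

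**Step 3: Part 5 with G100 stopped early.** Section 10.3.25 lets G100 be cancelled while rituximab continues. With last rituximab on Day 21, contraception under 7.1 runs to Day 111, but the 12.1 clock starts at the last G100 dose:

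- last G100 Day 14: 111 − 44 = 67 days
- last G100 Day 7: 111 − 37 = 74 days
- last G100 Day 1: 111 − 31 = 80 days

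**Step 4: a side issue, only if 12.1 means the date of report.** After six doses in Parts 1 to 3, the Day 77 test is 77 − 35 = 42 days after the last G100 (33 to 51 with windows), so a positive result falls outside unless dosing was delayed. In Part 5 after four doses, the Day 56 test is 56 − 21 = 35 days after (26 to 44), so it may fall either side.

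**The case against.** The best case for the plan is that several other routes reach the Sponsor, and that a precautionary contraception period may reasonably outlast a reporting period.

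- **12.7, all subjects.** Its heading is general, 12.1 refers to it, and a site could apply the follow-up and 24-hour outcome sentences to everyone. This stands as a possible reading, but the paragraph is introduced as a pembrolizumab rule and gives other patients no dated window.
- **Congenital anomaly.** It is an SAE under 12.1. Section 12.4 requires a possibly related SAE to be reported whenever it becomes known, and 12.3 tells investigators to lean towards relatedness and seriousness. This stands, and protects the most serious outcome. It does not capture the pregnancy itself or a normal outcome.
- **Protocol deviations.** Section 13.0 has all deviations forwarded to the sponsor, so failure to use contraception would get there. It sets no deadline and misses contraceptive failure despite compliance.
- **Contact and tests.** Sections 11.0 and 12.7 tell women to contact the investigator, so the site may know; in Parts 1 to 3 the Day 112 visit falls before contraception ends. Scheduled results reach the Sponsor on case report forms, though not as a timely pregnancy report.
- **Consistency.** One month matches the 30-day adverse event collection in 12.4. But for pembrolizumab the protocol itself aligns pregnancy reporting with contraception rather than with the 30-day period, unless new therapy starts.

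Appendix E, which holds the SAE reporting information, is not in the public copy, so the point is limited to the visible text.

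**Conclusion.** The point holds in a limited form. For women on G100 alone or G100 plus rituximab, 60 of the 90 contraception days carry no clear, dated duty to report a pregnancy to the Sponsor as such; in Part 5 this becomes 67 to 80 days if G100 stops after Day 14, 7 or 1 and rituximab runs to Day 21. The frequency of that is not given.

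A reader might infer that there is no duty at all, or that harm to a fetus would go unreported. The documents do not support either: the undated 12.7 wording, the SAE rule and the deviation rule each cover part of the ground. Nor are conceptions on treatment or partner pregnancies uncovered, since 8.1.10 deals with both.

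The result assumes a 30-day month and a contraception clock that runs from the later of G100 and rituximab, as 7.1 implies. The number of women affected is not given and is probably small. No endpoint, dose decision or statistical figure changes. This is a cheap improvement to safety reporting.

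**What to change.** - **12.1:** for patients not on pembrolizumab, require Sponsor reporting of any pregnancy that occurs from first dose to at least 90 days after the last dose of G100 or rituximab, whichever is later. Keying the rule to occurrence also removes the doubt over the date of report.
- **12.7:** align the one-month sentence with that window, and state that pregnancy follow-up and outcome reporting apply to all subjects.
- **8.1.9:** word the 90-day period to include G100 plus rituximab, in line with inclusion criteria 7 and 8.

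The uncovered interval then falls from 60 days to 0. The cost is wording in three sections and a line in the site instructions, with at most a few more pregnancy reports and no extra visits or tests. SAP Section 9 records that the sponsor terminated the study, so the practical use is an instruction to sites for women still within 90 days of dosing, and corrected text for any later G100 protocol.

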12.2 Adverse Event Severity

All AEs will be evaluated according to the NCI CTCAE v4.03 or newer (2010)

http://evs.nci.nih.gov/ftp1/CTCAE/CTCAE_4.03_2010-06-14_QuickReference_8.5x11.pdf. For AEs not listed in this reference scale, severity will be assessed by the investigator according to the criteria in [Table 5](#).

Table 5: Adverse Event Severity Assessment

Grade 1 (Mild)	Mild; asymptomatic or mild symptoms; clinical or diagnostic observations only; intervention not indicated.
Grade 2 (Moderate)	Moderate; minimal, local or noninvasive intervention indicated; limiting age-appropriate instrumental ADL*.
Grade 3 (Severe)	Severe or medically significant but not immediately life-threatening; hospitalization or prolongation of hospitalization indicated; disabling; limiting self-care activities of daily living (ADL)**.
Grade 4 (Life threatening)	Life-threatening consequences; urgent intervention indicated.
Grade 5 (Death)	Death related to AE.

*Instrumental ADL refer to preparing meals, shopping for groceries or clothes, using the telephone, managing money, etc.

**Self-care ADL refer to bathing, dressing and undressing, feeding self, using the toilet, taking medications, and not bedridden.

Changes in the severity of an AE should be documented to enable an assessment of the duration of the event at each level of intensity. Adverse events characterized as intermittent require documentation of onset and duration of each episode.

12.3 Relationship to Investigational Drug

The investigator will report his or her interpretation of the relationship between an AE and the study treatment on the basis of their clinical judgment and the definitions in Table 6.

Table 6: Assessment of Relationship

Definitely related	AEs clearly attributable to study regimen administration
Probably related	AEs for which there is a reasonable possibility of causal association to study regimen
Possibly related	AEs for which there is confounding by comorbidities, medications or other considerations but for which it is not unreasonable that the AE may have been caused by study regimen. Note that it is not appropriate to invoke “you can’t rule it out.”
Not related	AEs that are considered clearly not causally related to study regimen, or for which there is a clear alternative explanation

AE = adverse event

If there is any question whether or not an AE is possibly, probably or definitely related, the investigator should default to conservatism in categorization. Similarly, the investigator should default to conservatism by calling an AE an SAE if there is doubt regarding the serious nature of an AE, if it meets one of the definitions described above.

12.4 Adverse Event Collection Period

All enrolled patients in Parts 1, 2, 3, 4, and 5 will have periodic assessment of clinical and laboratory AEs. All AEs will be collected at the EOS / Post-Vaccination Safety Visit and for 30 days after the last dose of study agent whichever is longer (if receiving pembrolizumab, see below). Thereafter, any SAE that comes to the attention of the site staff that may be causally related to study drug (i.e., the event is considered possibly, probably or definitely caused by the drug) must be reported to Sponsor regardless of time elapsed.

Patients who withdraw from the study prior to the EOS Visit should be followed for new AEs for at least 30 days after their last dose of G100. If the subject withdraws prematurely and is unwilling to continue safety follow-up, any subsequent SAE that may be causally related to G100 that comes to the attention of the site staff should be reported to Immune Design.

For patients receiving pembrolizumab, any serious AE, or follow up to a serious AE, including death due to any cause other than progression of the cancer under study that occurs through 90 days following cessation of treatment, or 30 days following cessation of treatment if the subject initiates new anticancer therapy, whichever is earlier, must be reported within 24 hours to the Sponsor either by electronic media or paper. In addition, any event of clinical interest (ECI) experienced through 30 days following cessation of treatment should be reported within 24 hours to the Sponsor.

For Pembrolizumab:

- All AEs or ECIs (Events of Clinical Interest) from the time of treatment/ allocation through 30 days following cessation of study treatment must be reported by the investigator.
- All AEs meeting serious criteria, from the time of treatment/ allocation through 90 days following cessation of study treatment, or 30 days following cessation of study treatment if the participant initiates new anticancer therapy, whichever is earlier must be reported by the investigator
- All pregnancies and exposure during breastfeeding, from the time of treatment/ allocation through 120 days following cessation of study treatment, or 30 days following cessation of study treatment if the participant initiates new anticancer therapy must be reported by the investigator.

- Additionally, any SAE brought to the attention of an investigator at any time outside of the time period specified above must be reported immediately to the Sponsor if the event is considered to be drug-related.

